1.0 Definition of Analysis Sets and Terms and Handling of Test/Measurement Data

1.1 Analysis sets

1.1.1 Safety analysis set

In this survey, the safety analysis set is defined as patients treated with Adcetris IV Infusion with no major protocol violation and evaluable for safety.

1.1.2 Efficacy analysis set

In this survey, the efficacy analysis set is defined as patients treated with Adcetris IV Infusion with no major protocol violation and evaluable for efficacy.

Definition

Term	Definition
This/the product	Refers to Adcetris for intravenous drip infusion in this Statistical Analysis Plan.
SOC	MedDRA/J System Organ Class
HLGT	MedDRA/J High Level Group Term
PT	MedDRA/J Preferred Term
LLT	MedDRA/J Lowest Level Term
Patients registered	Patients whose registration has been approved
Patients whose case report forms are available	Patients whose case report forms have been collected
Patients whose case report forms are not available	Patients registered but whose case report form have not been collected
Fixed patients	Patients whose case report forms are available, with the date of case report form completion entered in the PMS system
Non-fixed patients	Patients whose case report forms are available, with the date of case report form completion not entered in the PMS system
Safety analysis set	Fixed patients included in the safety analysis set
Safety analysis set (Hodgkin's lymphoma)	Patients included in the safety analysis set whose diagnosis is Hodgkin's lymphoma
Safety analysis set (anaplastic large-cell lymphoma)	Patients included in the safety analysis set whose diagnosis is anaplastic large-cell lymphoma
Patients excluded from the safety analysis set	Fixed patients excluded from the safety analysis set
Efficacy analysis set	Patients included in the safety analysis set who are also included in the efficacy analysis set
Patients excluded from the efficacy analysis set	Patients included in the safety analysis set who are excluded from the efficacy analysis set
Patients completing treatment	Patients completing 16 cycles of treatment with Adcetris
Patients discontinuing treatment	Patients not completing 16 cycles of treatment with Adcetris

Term	Definition
Adverse drug reactions, etc.	
Refers to “adverse drug reactions and infections.”
 
Adverse events not considered “not related” to Adcetris by the investigator.
 
In this Statistical Analysis Plan, the term “adverse drug reactions and infections” is used in titles and the term “adverse drug reactions, etc.” is used in text and tables.

Serious adverse events	
Adverse events considered “serious” by the investigator.
 
Events listed in the MedDRA Coding List in the Takeda Medically Significant AE List should be regarded as serious even if they are considered “non-serious” by the investigator.

Number of patients with adverse events/adverse drug reactions	Number of patients experiencing adverse events or adverse drug reactions, etc.
Number of adverse events/adverse drug reactions	Number of adverse events or adverse drug reactions, etc., observed
Percentage of patients with adverse events/adverse drug reactions	
[For safety analysis using patients included in the safety analysis set]
 
Is calculated using the following formula: (number of patients with adverse events/adverse drug reactions) / (number of patients included in the safety analysis set) × 100.
 
[For safety analysis using patients excluded from the safety analysis set]
 
Is calculated using the following formula: (number of patients with adverse events/adverse drug reactions) / (number of patients excluded from the safety analysis set) × 100.

Percentage of adverse events/adverse drug reactions observed	
[For safety analysis using patients included in the safety analysis set]
 
Is calculated using the following formula: (number of adverse events/adverse drug reactions observed) / (number of patients included in the safety analysis set) × 100.
 
[For safety analysis using patients excluded from the safety analysis set]
 
Is calculated using the following formula:(number of adverse events/adverse drug reactions observed) / (number of patients excluded from the safety analysis set) × 100.

Time of onset	
Is calculated using the following formula: date of onset of adverse events (or adverse drug reactions, etc.) – date of the initial dose of Adcetris + 1.
 
If the day, month, and year of onset of adverse events (or adverse drug reactions, etc.) are unknown, the time of onset should be handled as missing, and the category for the time of onset should be “unknown.”

Time to the worst grade	Is calculated using the following formula: date of the worst CTCAE grade – date of the initial dose of Adcetris + 1.

Term	Definition																									
	If the day, month, and year of the worst CTCAE grade are unknown, the date of the worst CTCAE grade should be handled as missing, and the category for the date of the worst CTCAE grade should be “unknown.”																									
Patients with concurrent hepatic disorder	Patients having a concurrent illness that falls under the category of Standardized MedDRA Query (SMQ) Code 20000005 (SMQ Hepatic disorders [Scope: Narrow])																									
Grade of hepatic disorder	
The ALT or AST level at baseline with the highest grade will be used to determine the grade of hepatic disorder. The grades of ALT and AST levels will be determined according to the following tables, and the grade should be “unknown” if either the ALT or AST level is missing:
 
ALT
 
  
 	Male	Female	
   
 None	≤42 IU/L	≤23 IU/L	
 
 Grade 1	>42 to ≤126 IU/L	>23 to ≤69 IU/L	
 
 Grade 2	>126 to ≤210 IU/L	>69 to ≤115 IU/L	
 
 ≥Grade 3	>210 IU/L	>115 IU/L	
  
 
AST
 
  
 		
   
 None	≤30 IU/L	
 
 Grade 1	>30 to ≤90 IU/L	
 
 Grade 2	>90 to ≤150 IU/L	
 
 ≥Grade 3	>150 IU/L	
  
		Male	Female	None	≤42 IU/L	≤23 IU/L	Grade 1	>42 to ≤126 IU/L	>23 to ≤69 IU/L	Grade 2	>126 to ≤210 IU/L	>69 to ≤115 IU/L	≥Grade 3	>210 IU/L	>115 IU/L			None	≤30 IU/L	Grade 1	>30 to ≤90 IU/L	Grade 2	>90 to ≤150 IU/L	≥Grade 3	>150 IU/L
	Male	Female																								
None	≤42 IU/L	≤23 IU/L																								
Grade 1	>42 to ≤126 IU/L	>23 to ≤69 IU/L																								
Grade 2	>126 to ≤210 IU/L	>69 to ≤115 IU/L																								
≥Grade 3	>210 IU/L	>115 IU/L																								
None	≤30 IU/L																									
Grade 1	>30 to ≤90 IU/L																									
Grade 2	>90 to ≤150 IU/L																									
≥Grade 3	>150 IU/L																									
Patients with concurrent renal disorder	Patients having a concurrent illness that falls under the category of Takeda MedDRA Query (TMQ) (Renal disease)																									
Grade of renal disorder	
The serum creatinine level at baseline will be classified as shown in the table below. If the serum creatinine level at baseline is missing, the grade of renal disorder should be “unknown.”
 
Serum creatinine
 
  
 	Male	Female	
   
 None	≤1.07 mg/dL	≤0.79 mg/dL	
 
 Grade 1	>1.07 to ≤1.605 mg/dL	>0.79 to ≤1.185 mg/dL	
 
 Grade 2	>1.605 to ≤3.21 mg/dL	>1.185 to ≤2.37 mg/dL	
 
 ≥Grade 3	>3.21 mg/dL	>2.37 mg/dL	
  
		Male	Female	None	≤1.07 mg/dL	≤0.79 mg/dL	Grade 1	>1.07 to ≤1.605 mg/dL	>0.79 to ≤1.185 mg/dL	Grade 2	>1.605 to ≤3.21 mg/dL	>1.185 to ≤2.37 mg/dL	≥Grade 3	>3.21 mg/dL	>2.37 mg/dL										
	Male	Female																								
None	≤1.07 mg/dL	≤0.79 mg/dL																								
Grade 1	>1.07 to ≤1.605 mg/dL	>0.79 to ≤1.185 mg/dL																								
Grade 2	>1.605 to ≤3.21 mg/dL	>1.185 to ≤2.37 mg/dL																								
≥Grade 3	>3.21 mg/dL	>2.37 mg/dL																								
Patients with a past history of pulmonary disorder	
Patients with a past history that falls under the category of Appendix “Definition of Pulmonary Disorders”
 
(If “No concurrent illness existed at the initiation of treatment with Adcetris” is selected in the field of “Past history/concurrent illness of pulmonary disorders” in the case report form, the pulmonary disorder
																									

Term	Definition
	should be regarded as a past history.)
Patients with concurrent pulmonary disorder	Patients with a concurrent illness that falls under the category of Appendix “Definition of Pulmonary Disorders” (If “A concurrent illness existed at the initiation of treatment with Adcetris” is selected in the field of “Past history/concurrent illness of pulmonary disorders” in the case report form, the pulmonary disorder should be regarded as a concurrent illness.)
Patients with a past history of malignant tumour	Patients with a past history that falls under the category of MedDRA SMQ Code 20000194 (SMQ Malignant tumours [Scope: Narrow]) (If “No concurrent illness existed at the initiation of treatment with Adcetris” is selected in the field of “Past history/concurrent illness of malignant tumours” in the case report form, the pulmonary disorder should be regarded as a past history.)
Patients with concurrent malignant tumour	Patients with a concurrent illness that falls under the category of MedDRA SMQ Code 20000194 (SMQ Malignant tumours [Scope: Narrow]) (If “A concurrent illness existed at the initiation of treatment with Adcetris” is selected in the field of “Past history/concurrent illness of malignant tumours” in the case report form, the pulmonary disorder should be as a concurrent illness.)
Patients with concurrent diabetes mellitus	Patients with a concurrent illness that falls under the category of MedDRA SMQ Code 20000041 (SMQ Hyperglycaemia/new onset diabetes mellitus [Scope: Narrow])
Patients with hypertension	Patients with a concurrent illness that falls under the category of MedDRA SMQ Code 20000147 (SMQ Hypertension [Scope: Narrow])
Patients with concurrent dyslipidaemia	Patients with a concurrent illness that falls under the category of MedDRA SMQ Code 20000026 (SMQ Dyslipidaemia [Scope: Narrow])
Patients with concurrent hyperuricaemia	Patients with a concurrent illness that falls under the category of MedDRA PT Code 10020903 (Hyperuricaemia)
Patients with concurrent infection	Patients with a concurrent illness that falls under the category of MedDRA SOC Code 10021881 (Infections and infestations)
Patients with concurrent peripheral neuropathy	Patients with a concurrent illness that falls under the category of SMQ Code 20000034 (SMQ Peripheral neuropathy [Scope: Narrow])
Patients with other concurrent illnesses	Patients with any concurrent illness other than those listed above
Antibiotics/synthetic antibacterial agents	Drugs with the first three digits of YJ Code being either one of 611 to 616, 619, or 624 that are entered in the field of “Drugs used for the prevention of infection” (If more than one antibiotics/synthetic antibacterial agents are used in the same patient, it will be counted as one patient.)
Antifungals	Drugs with the first three digits of YJ Code being 617 or the first seven

Term	Definition
	digits being 6290002 or 6290004 that are entered in the field of “Drugs used for the prevention of infection” (If more than one antifungals are used in the same patient, it will be counted as one patient.)
Antivirals	Drugs with the first three digits of YJ Code being 625 that are entered in the field of “Drugs used for the prevention of infection” (If more than one antivirals are used in the same patient, it will be counted as one patient.)
Trimethoprim-sulfamethoxazole combinations	Drugs with YJ Code being 62901000 that are entered in the field of “Drugs used for the prevention of infection” (If more than one trimethoprim-sulfamethoxazole combinations are used in the same patient, it will be counted as one patient.)
Other prophylactics against infections	Any drug entered in the field of “Drugs used for the prevention of infection” other than prophylactics against infections listed above (If more than one other prophylactics against infections are used in the same patient, it will be counted as one patient.)
Peripheral sensory neuropathy (as an adverse event)	Adverse events with “Sensory neuropathy” entered in the “Category of peripheral nerve disorders” in the field of “Adverse events: [1] Peripheral nerve disorders] in the case report form. MedDRA PT Code 10034620 should be assigned regardless of data entered in “Symptoms” in the field.
Peripheral motor neuropathy (as an adverse event)	Adverse events with “Motor neuropathy” entered in the “Category of peripheral nerve disorders” in the field of “Adverse events: [1] Peripheral nerve disorders] in the case report form. MedDRA PT Code 10034580 should be assigned regardless of data entered in “Symptoms” in the field.
Peripheral neuropathy (as an adverse event)	Adverse events with “Other” entered in the “Category of peripheral nerve disorders” in the field of “Adverse events: [1] Peripheral nerve disorders] in the case report form. MedDRA PT Code 10029331 should be assigned, regardless of data entered in “Symptoms” in the field.
Pulmonary disorders (as adverse events)	Adverse events that fall under the category of Appendix “Definition of Pulmonary Disorders”
Infusion reaction (as an adverse event)	MedDRA PT Code 10051792 (Infusion related reaction) will be assigned, regardless of symptoms entered in the field of “Adverse events: [4] Infusion reaction.”
Patients with the onset of infection	Patients with adverse drug reactions that fall under the category of MedDRA SOC Code 10021881 (Infections and infestations)
Patients with the onset of bacterial infection	Patients with adverse drug reactions that fall under the category of MedDRA HLTG Code 10004018 (Bacterial infection), 10008555 (Chlamydial infection), 10028474 (Mycoplasma infection) or 10039135 (Rickettsia infection)
Patients with the onset of fungal infection	Patients with adverse drug reactions that fall under the category of MedDRA HLTG Code 10017528 (Fungal infection)

Term	Definition										
Patients with the onset of viral infection	Patients with adverse drug reactions that fall under the category of MedDRA HLG Code 10047438 (Viral infection)										
Age	
If the month and day of the initial dose of Adcetris is < the month and day of birth, the patient's age will be calculated using the following formula: Year of the initial dose of Adcetris – year of birth – 1.
 
If the month and day of the initial dose of Adcetris is ≥ the month and day of birth, the patient's age will be calculated using the following formula: Year of the initial dose of Adcetris – year of birth.
 
If the month and day of birth are unknown, they should be “January 1,” and if the day of birth is unknown, it should be the first day of the month.
 
If the day, month, and year of birth are unknown but the patient's age is known, the patient's age should be used as it is.
										
BMI	BMI should be calculated using the following formula: Weight (kg)/(0.0001 × height (cm) × height (cm)). The obtained value should be rounded off to one decimal place.										
Disease duration	
The disease duration should be calculated using the following formula: [“Date of the initial dose of Adcetris” – “date of diagnosis of Hodgkin's or anaplastic large-cell lymphoma” +1]/365.25.
 
The day of diagnosis should be the first day of the month provided. If the month of diagnosis is unknown, the date of diagnosis should be “January 1st” of the year provided.
										
Mean dose of Adcetris	Is calculated as the total value of each dose of Adcetris given at each treatment cycle divided by the number of cycles.										
Dose of Adcetris per 3 weeks	
Is calculated using the following formula: Total “dose of Adcetris”/([“date of the last dose of Adcetris” – “date of the initial dose of Adcetris” + 21)/21].
 
If only 1 cycle of treatment is given, the “date of the last dose of Adcetris” and the “date of the initial dose of Adcetris” should be regarded as the same.
										
Degree of decreased neutrophil count at baseline	
The neutrophil count at baseline will be classified as shown in the table below. If the neutrophil count at baseline is missing, the degree of the neutrophil count at baseline should be handled as missing:
 
  
 No decrease	≥2,000 /mm³	
 
 Grade 1	≥1,500 to <2,000 /mm³	
 
 Grade 2	≥1,000 to <1,500 /mm³	
 
 Grade 3	≥500 to <1,000 /mm³	
 
 Grade 4	<500 /mm³	
  
	No decrease	≥2,000 /mm ³	Grade 1	≥1,500 to <2,000 /mm ³	Grade 2	≥1,000 to <1,500 /mm ³	Grade 3	≥500 to <1,000 /mm ³	Grade 4	<500 /mm ³
No decrease	≥2,000 /mm ³										
Grade 1	≥1,500 to <2,000 /mm ³										
Grade 2	≥1,000 to <1,500 /mm ³										
Grade 3	≥500 to <1,000 /mm ³										
Grade 4	<500 /mm ³										
Days from the month of the completion of the final regimen	Is calculated using the following formula: date of the initial dose of Adcetris – date of the completion of the final regimen of prior drug										

Term	Definition
of prior drug therapy to the date of 1 cycle of treatment with Adcetris	therapy + 1. If the month of “the completion of the final regimen of prior drug therapy” is missing, the date of the completion of the final regimen of prior drug therapy should be handled as missing.
Days from the month of the completion of the most recent prior radiotherapy to the date of 1 cycle of treatment with Adcetris	Is calculated using the following formula: date of the initial dose of Adcetris – date of the completion of the most recent prior radiotherapy + 1. If the month of “the completion of the most recent prior radiotherapy” is missing, the date of the completion of the most recent prior radiotherapy should be handled as missing.
Days from the date of the last dose of Adcetris to hematopoietic stem cell transplantation (autologous) (Post-baseline hematopoietic stem cell transplantation: autologous)	For patients with post-baseline hematopoietic stem cell transplantation (autologous), this data item will be calculated using the following formula: date of post-baseline hematopoietic stem cell transplantation (autologous) – date of the last dose of Adcetris + 1. If the date of post-baseline hematopoietic stem cell transplantation (autologous) is missing, this data item should be handled as missing. For patients with no post-baseline hematopoietic stem cell transplantation (autologous), this data item should be handled as missing.
Duration of treatment with Adcetris prior to hematopoietic stem cell transplantation (autologous) (Post-baseline hematopoietic stem cell transplantation: autologous)	For patients with post-baseline hematopoietic stem cell transplantation (autologous), this data item will be calculated using the following formula: date of the last dose of Adcetris – date of the initial dose of Adcetris + 1. If the date of post-baseline hematopoietic stem cell transplantation (autologous) is missing, this data item should be handled as missing. For patients with no post-baseline hematopoietic stem cell transplantation (autologous), this data item should be handled as missing.
Days from the date of the last dose of Adcetris to hematopoietic stem cell transplantation (homologous) (Post-baseline hematopoietic stem cell transplantation: homologous)	For patients with post-baseline hematopoietic stem cell transplantation (homologous), this data item will be calculated using the following formula: date of hematopoietic stem cell transplantation (homologous) – date of the last dose of Adcetris + 1. If the date of post-baseline hematopoietic stem cell transplantation (homologous) is missing, this data item should be handled as missing. For patients with no post-baseline hematopoietic stem cell transplantation (homologous), this data item should be handled as missing.
Duration of treatment with Adcetris prior to hematopoietic stem cell transplantation (homologous) (Post-baseline hematopoietic stem cell transplantation: stem cell transplantation: homologous)	For patients with post-baseline hematopoietic stem cell transplantation (homologous), this data item will be calculated using the following formula: date of the last dose of Adcetris – date of the initial dose of Adcetris + 1. If the date of post-baseline hematopoietic stem cell transplantation (homologous) is missing, this data item should be handled as missing.

Term	Definition
homologous)	For patients with no post-baseline hematopoietic stem cell transplantation (homologous), this data item should be handled as missing.
Date of the final observation	“Date of the final observation” in the case report form If not provided, the most recent date entered in the case report form should be used.
Summary statistics	Number of patients, mean, standard deviation, minimum, 25th percentile, median, 75th percentile, and maximum.
Overall survival	Time to the date of death from any cause after the date of the initial dose of Adcetris. Surviving patients will be censored on the date of survival confirmation. The date of outcome of an adverse event with “Died/fetal” recorded in the Outcome field will be used as the date of death, and the final observation date will be used as the date of survival confirmation. The overall survival (date of death or survival confirmation) = date of death or survival confirmation – date of the initial dose of Adcetris+1
1 year	One year is defined as 365.25 days.
1 month	One month is defined as 30.4375 days.

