1.4 Handling of test data

Test data will be handled according to the criteria shown below. If there are multiple data for the same criterion, the one with the test date being closest to the date of protocol-specified assessment should be used. If there is no difference in the number of days from the date of protocol-specified assessment, the later value should be used.

The number of days after the date of the initial dose of Adcetris is defined as 1 for the date of the initial dose of Adcetris and 0 for the day before the date of the initial dose of Adcetris.

Time point for testing	Date of protocol-specified assessment	Acceptable time window
At the initial dose of Adcetris	Date of the initial dose of Adcetris	-15 days to the date of the initial dose of Adcetris
After 1 cycle	
 If Cycle 2 is initiated: Date of Cycle 2 If Cycle 2 is not initiated: 21 days after the date of the initial dose of Adcetris 	
 If Cycle 2 is initiated: Date of Cycle 2 If Cycle 2 is not initiated: 21 days after the date of the initial dose of Adcetris

Time point for testing	Date of protocol-specified assessment	Acceptable time window
After 2 cycles	
 • If Cycle 3 is initiated: Date of Cycle 3 • If Cycle 3 is not initiated: 21 days after the date of Cycle 2 	
 • If Cycle 3 is initiated: From the day after the date of Cycle 2 to the day of Cycle 3 • If Cycle 3 is not initiated: From the day after the date of Cycle 2 to 21 days after the date of Cycle 2
After 3 cycles	
 • If Cycle 4 is initiated: Date of Cycle 4 • If Cycle 4 is not initiated: 21 days after the date of Cycle 3 	
 • If Cycle 4 is initiated: From the day after the date of Cycle 3 to the day of Cycle 4 • If Cycle 4 is not initiated: From the day after the date of Cycle 3 to 21 days after the date of Cycle 3
After 4 cycles	
 • If Cycle 5 is initiated: Date of Cycle 5 • If Cycle 5 is not initiated: 21 days after the date of Cycle 4 	
 • If Cycle 5 is initiated: From the day after the date of Cycle 4 to the day of Cycle 5 • If Cycle 5 is not initiated: From the day after the date of Cycle 4 to 21 days after the date of Cycle 4

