1.5 Handling of missing data

- As a general rule, missing data will not be imputed.
- In the analysis of the frequency qualitative variables, missing data will be handles as “unknown.” In the analysis of summary statistics of quantitative variables, missing data will be excluded.

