4.3 Patient demographics and baseline characteristics by initial dose of Adcetris

(1) Analysis sets to be used

Patients included in safety evaluation and patients included in safety evaluation (Hodgkin's lymphoma) or patients included in safety evaluation (anaplastic large-cell lymphoma)

(2) Data to be analyzed

For each data item, patients will be stratified into the following categories, and the frequency will be calculated by initial dose of Adcetris (<1.2 mg/kg, 1.2 mg/kg, >1.2 mg/kg to <1.8 mg/kg, 1.8 mg/kg, or >1.8 mg/kg):

Data item	Category
Age	<18 years, 18 to 39 years, 40 to 64 years, 65 to 74 years, or ≥75 years
ECOG Performance Status	0, 1, 2, 3, or 4
Concurrent hepatic disorders	Absent or present
Grade of hepatic disorder (Grade based on AST)	None, Grade 1, Grade 2, ≥Grade 3, or unknown

Data item	Category
and ALT levels)	
Concurrent renal disorders	Absent or present
Grade of renal disorder (Grade based on serum creatinine)	None, Grade 1, Grade 2, \geq Grade 3, or unknown
Concurrent infection	Absent or present
Concurrent peripheral nerve disorder	None, Grade 1, Grade 2, Grade 3, Grade 4, or unknown

(3) Figure/table number

Tables 4.3-1 to 4.3-3

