5.2.4 Occurrence of adverse drug reactions/infections by CTCAE Grade (the worst one)

(1) Analysis sets to be used

Safety analysis set, safety analysis set (Hodgkin’s lymphoma), and safety analysis set (anaplastic large-cell lymphoma)

(2) Data to be analyzed

For each data item, patients will be stratified into the following categories, and the type of adverse drug reactions, etc., will be analyzed:

Data item	Category
CTCAE Grade (the worst one)	≤Grade 2, ≥Grade 3, or unknown

The type of adverse drug reactions, etc., will be analyzed as follows:

Data item	Data to be analyzed
Type of adverse drug reactions, etc.	The incidence of adverse drug reactions, etc., for each CTCAE grade (the worst one) will be calculated by SOC and PT. For SOC, the number and percentage of patients with drug reactions, etc., will be calculated. For PT, the number and percentage of drug reactions, etc., will be calculated. SOCs will be presented in the internationally agreed order, and PTs will be presented in ascending order of HLGT and PT codes if their SOCs are “Investigations,” and in ascending order of PT code otherwise. The CTCAE grade (the worst one) is higher in the order of ≥Grade 3, ≤Grade 2, and unknown. If the same patient has multiple occurrences of the same adverse drug reaction, etc. (PT), the reaction with the highest CTCAE grade will be counted once per patient.

(3) Figure/table number

Tables 5.2.4-1 to 5.2.4-3

5.3 Percentage of patients with adverse drug reactions/infections by patient demographics and baseline characteristics and treatment given

(1) Analysis sets to be used

Safety analysis set, safety analysis set (Hodgkin’s lymphoma), and safety analysis set (anaplastic large-cell lymphoma)

(2) Data to be analyzed

For each data item, patients will be stratified into the following categories, and the percentage of patients with adverse drug reactions, etc. (with point estimate and 95% confidence interval) will be determined.

For categories associated and not associated with ranking, Fisher’s exact and Mann-Whitney U tests, respectively, will be used. If there is a category of “unknown,” it will be excluded to perform

the Mann-Whitney U test.

Data item	Category
Sex	Male or female
Age	<18 years, 18 to 64 years, 65 to 74 years, or ≥ 75 years
Disease duration	<1 year, <1 to 3 years, <3 to 5 years, ≥ 5 years, or unknown
ALK (for patients with anaplastic large-cell lymphoma)	Positive, negative, or unknown
Clinical stage	I, II, III, IV, or unknown

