B symptoms	Absent or present
ECOG Performance Status	0, 1, 2, 3, or 4
Past history of pulmonary disorders	Absent or present
Concurrent pulmonary disorders	Absent or present
Past history of malignant tumours	Absent or present
Concurrent malignant tumours	Absent or present
Concurrent hepatic disorders	Absent or present
Grade of hepatic disorder (Grade based on AST and ALT levels)	None, Grade 1, Grade 2, \geq Grade 3, or unknown
Concurrent renal disorders	Absent or present
Grade of renal disorder (Grade based on serum creatinine)	None, Grade 1, Grade 2, \geq Grade 3, or unknown
Weight	<40 kg, <40 to 50 kg, <50 to 60 kg, <60 to 70 kg, or ≥ 70 kg
BMI	<18.5 kg/m ² , <18.5 to 25 kg/m ² , <25 to 30 kg/m ² , or ≥ 30 kg/m ²
Smoking history	Never, current, past, or unknown
Prior drug therapy	Absent or present
Prior radiotherapy	Absent or present
Prior hematopoietic stem cell transplantation	Absent, present (autologous), present (homologous), present (autologous and homologous), or unknown
Initial dose of Adcetris	<1.2 mg/kg, 1.2 mg/kg, >1.2 mg/kg to <1.8 mg/kg, 1.8 mg/kg, or >1.8 mg/kg

Data item	Category
Mean dose of Adcetris	<1.2 mg/kg, 1.2 mg/kg, >1.2 mg/kg to <1.8 mg/kg, 1.8 mg/kg, or >1.8 mg/kg
Dose of Adcetris per 3 weeks	<1.2 mg/kg, 1.2 mg/kg, >1.2 mg/kg to <1.8 mg/kg, 1.8 mg/kg, or >1.8 mg/kg
Drug(s) other than Adcetris used for the treatment of the primary disease	Absent or present

(3) Figure/table number

Tables 5.3-1 to 5.3-3

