5.4 Occurrence of adverse drug reactions/infections by age group

(1) Analysis sets to be used

Safety analysis set, safety analysis set (Hodgkin's lymphoma), and safety analysis set (anaplastic large-cell lymphoma)

(2) Data to be analyzed

The similar calculation as the one described in Section 5.1.2, will be performed by age group (<18 years, 18 to 64 years, 65 to 74 years, or ≥ 75 years).

The type of adverse drug reactions, etc., will be analyzed in the same manner as described in Section 5.1.

(3) Figure/table number

Tables 5.4-1 to 5.4-3

5.5 Occurrence of adverse drug reactions/infections by presence or absence and grade of concurrent hepatic disorder

(1) Analysis sets to be used

Safety analysis set, safety analysis set (Hodgkin's lymphoma), and safety analysis set (anaplastic large-cell lymphoma)

(2) Data to be analyzed

The similar calculation as the one described in Section 5.1.2, will be performed by presence or absence and grade of concurrent hepatic disorder.

The type of adverse drug reactions, etc., will be analyzed in the same manner as described in Section 5.1.

(3) Figure/table number

Tables 5.5-1 to 5.5-3

5.6 Occurrence of adverse drug reactions/infections by presence or absence and grade of concurrent renal disorder

(1) Analysis sets to be used

Safety analysis set, safety analysis set (Hodgkin's lymphoma), and safety analysis set (anaplastic large-cell lymphoma)

(2) Data to be analyzed

The similar calculation as the one described in Section 5.1.2, will be performed by presence or absence and grade of concurrent renal disorder

The type of adverse drug reactions, etc., will be analyzed in the same manner as described in Section 5.1.

(3) Figure/table number

Tables 5.6-1 to 5.6-3

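### Hepatic grade becomes 'unknown' when one of ALT or AST is missing, even if the other is already ≥Grade 3 and the grade is therefore known

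*SAP*

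**What the plan says.** The entry for grade of hepatic disorder in the SAP definitions table (section 1.0) gives two rules.

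- Combining rule: "The ALT or AST level at baseline with the highest grade will be used to determine the grade of hepatic disorder".
- Missing-value rule: the grade is 'unknown' "if either the ALT or AST level is missing". No exception is made for an observed value that is already in the top category.

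The cut-offs make ≥Grade 3 open-ended: ALT above 210 IU/L in men or above 115 IU/L in women, or AST above 150 IU/L. The baseline laboratory window in SAP 1.4 runs from day -15, that is, minus "15 days to the date of the initial dose of Adcetris". I take 'missing' to mean no value in that window. SAP 1.5 adds the general rule: "As a general rule, missing data will not be imputed".

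The grade is used in four places. SAP 3.1, 4.3 and 5.3 tabulate it as "None, Grade 1, Grade 2, ≥Grade 3, or unknown". In 5.3 it is one of the factors against which the percentage of patients with adverse drug reactions is reported, with a 95% confidence interval for each category. SAP 5.5 repeats the adverse drug reaction tables, which "will be performed by presence or absence and grade of concurrent hepatic disorder"; it states no exclusion. On testing, 5.3 says of an 'unknown' category that "it will be excluded to perform" the Mann-Whitney U test.

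**The concern.** The two rules conflict in one situation. When the grade is a maximum and one component is already in the highest category, the other component cannot change the result. The grade is then known, and calling it 'unknown' discards a measured value that settles the matter.

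The loss has one direction. No other determinable grade is given up, so the rule can only take patients out of ≥Grade 3, the row most relevant to safety in patients with raised liver enzymes and probably a sparse one. As an illustration with assumed counts: if three patients were truly ≥Grade 3 and one of them lacked the second enzyme, the row would lose a third of its patients.

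The separate variable for concurrent hepatic disorder does not fully make up for this. It depends on a recorded illness that codes to the hepatic query, not on laboratory values. A man with ALT above 210 IU/L, no AST and no coded liver illness would be 'absent' on that variable and 'unknown' on grade. Neither classification would show the measured elevation.

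**Working it through.** The plan gives no sample size, power or expected count for the hepatic-grade analysis, so there is no figure to reproduce. The check is an enumeration of the rule, followed by a scale estimate.

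**1. Are the cut-offs consistent?** Each upper limit divided by the limit for 'None':
- ALT, men: 126/42 = 3 and 210/42 = 5
- ALT, women: 69/23 = 3 and 115/23 = 5
- AST: 90/30 = 3 and 150/30 = 5

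The grading table is consistent. The problem lies only in the missing-value rule.

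**2. Which grades remain possible when a value is missing?** Each enzyme has five states (None, 1, 2, ≥3, missing). That gives 5 × 5 = 25 combinations, of which 4 × 4 = 16 are complete and 9 have at least one value missing.

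| Observed enzyme | Other enzyme | Combinations | Possible maximum | SAP assigns |
|---|---|---|---|---|
| None | missing | 2 | None, 1, 2 or ≥3 | unknown |
| Grade 1 | missing | 2 | 1, 2 or ≥3 | unknown |
| Grade 2 | missing | 2 | 2 or ≥3 | unknown |
| ≥Grade 3 | missing | 2 | ≥3 only | unknown |
| both missing | | 1 | None, 1, 2 or ≥3 | unknown |

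'Unknown' is defensible in seven of the nine combinations, because the observed value gives only a lower bound or nothing. In the other two (ALT ≥Grade 3 with AST missing, and the reverse) only one grade is possible.

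**3. Where do these patients go?**
- SAP 3.1, 4.3 and 5.3: from the ≥Grade 3 row to the listed 'unknown' row.
- SAP 5.5: the same shift, with no exclusion stated.
- Test in 5.3: as printed, ranked categories go to Fisher's exact test and unranked ones to Mann-Whitney U, and 'unknown' is removed only for the latter. Hepatic grade is ranked, so on the literal text no exclusion is stated for it. If the two test names have been transposed, which is plausible, 'unknown' leaves the test.

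**4. How many patients?** The documents give no missingness rate. Let m be the share of patients with exactly one enzyme missing, and g the share of those whose observed enzyme is ≥Grade 3. Both are assumptions. With the planned 140 patients (Protocol 3.1), the expected number affected is 140 × m × g, and the chance of at least one is 1 − (1 − m × g)^140.

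| m | g | Expected | Chance of at least one |
|---|---|---|---|
| 1% | 1% | 140 × 0.01 × 0.01 = 0.014 | 1.4% |
| 5% | 5% | 140 × 0.05 × 0.05 = 0.35 | 29.6% |
| 10% | 10% | 140 × 0.10 × 0.10 = 1.4 | 75.5% |
| 20% | 10% | 140 × 0.20 × 0.10 = 2.8 | 94.1% |

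**The case against.** The strongest defence is that this is a simple complete-data rule. It treats every patient with one missing enzyme alike, and it accords with SAP 1.5, which does not impute and shows missing qualitative data as 'unknown'. ALT and AST stand in the same laboratory list in Protocol 9.2.4.1 and will usually be measured together. The surveillance is descriptive, and no decision rule or sample size depends on this grade.

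Most of that stands, and it keeps the point small. The appeal to SAP 1.5 does not: assigning ≥Grade 3 from an observed ≥Grade 3 value imputes nothing, because the measured value already determines the maximum.

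A reader might also infer something stronger, namely that patients with the worst liver values are dropped from the hepatic-risk analysis. The documents do not support that:

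- Anyone with both enzymes recorded is graded correctly, however high the values.
- The affected patients stay in the tables, in a reported 'unknown' row. They can leave only a significance test, and then only if the test assignment in 5.3 is read as transposed.
- Protocol 10.4.2 names the presence or absence of concurrent hepatic disorders. The SAP defines that from the recorded illness, so a missing enzyme cannot alter it. The laboratory grade is an additional SAP variable.

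**Conclusion.** The rule is wrong as written for two of the nine missing-value combinations: it loses a grade that the SAP's own highest-grade rule fully determines. The consequence is a shift from the ≥Grade 3 row to the 'unknown' row, not a removal from the analysis.

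The severity is low. The likely number is zero to a few patients (0.014 to 2.8 expected under the assumed ranges), and it cannot be derived from the documents. The scale also rests on 140 as the number analysed, which is the planned enrolment and may differ from the final safety analysis set. What does not depend on those assumptions is the direction: the error can only reduce the top category.

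**What to change.** Replace the missing-value sentence in the definition of hepatic grade with: *If one of ALT or AST is missing and the other is ≥Grade 3, the grade is ≥Grade 3; otherwise, if either is missing, the grade is unknown.* This changes the two determined combinations and leaves the other seven as they are.

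The cost is one sentence in the SAP and about one line of derivation code. There is one small downside: patients with a single enzyme would then be graded only when that value is in the top category, which slightly raises the ≥Grade 3 share among graded patients. Keeping the 'unknown' row in the tables, as already planned, lets a reader see this.

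Separately, the sentence in 5.3 that assigns the two tests should be reconciled, so that it is clear whether 'unknown' hepatic grades are excluded from a test at all.
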